5.4 Screen Failures

Screen failures are defined as subjects who consent to participate in the clinical study but are not subsequently enrolled in the study. A minimal set of screen failure information will be collected that includes demography, screen failure details, eligibility criteria, and any serious adverse events.

Individuals who do not meet the criteria for participation in this study (screen failure) may be rescreened **up to 2 times**. Refer to Section 8.1.1.

6. Treatments

Study treatment is defined as any investigational product(s), non-investigational product(s), placebo, **combination product**, or medical device(s) intended to be administered to a study subject according to the study protocol.

Note that in several countries, investigational product and non-investigational product are referred to as investigational medicinal product and non-investigational medicinal product, respectively.

The Investigational Product Instruction Manual (IPIM), a document external to this protocol, contains detailed information regarding the storage, preparation, destruction, and administration of each treatment (Table 6-1).

6.1 Treatment(s) Administered

6.1.1 Investigational Products

Study Treatment Name	Amgen Investigational Product: ^a AMG 510
Dosage Formulation	120 mg tablets
Unit Dose Strength(s)/ Dosage Level(s) and Dosage Frequency	960 mg QD, or 720 mg QD if dose modification is required (See Section 6.2)
Route of Administration	Oral
Accountability	The planned dose, start date/time, stop date, quantity administered, unit, planned frequency, reason for dose change/withheld, package lot number to be recorded on each subject's eCRF(s).
Dosing Instructions	AMG 510 will be administered orally QD for 21-day cycles, with no drug holidays between each cycle. The planned dose level(s) for AMG 510 will be dispensed at the research facility by a qualified staff member. Subjects are required to take AMG 510 at the research facility on clinic visit days as described in Table 1-1. Subjects will take AMG 510 at home on non-clinic visit days at approximately the same time(s) every day. The AMG 510 dose should also not be taken more than 2 hours earlier than the target time based on previous day's dose . AMG 510 must be administered in the fasted state (no food or liquids, except water, 2 hours before to 1 hour after dosing) until cycle 2 day 2 and beyond at which time they may take AMG 510 with approximately 240 mL (8 ounces) of water.
	The AMG 510 dose should not be taken more than 6 hours after the dosing time. Take the next dose as prescribed the next day. If vomiting occurs after taking AMG 510, do not take an additional dose. Take the next dose as prescribed the next day.
	Administration to patients who have difficulty swallowing solids: disperse tablets in 120 mL (4 ounces) of non-carbonated, room-temperature water without crushing. No other liquids should be used. Stir until tablets are dispersed into small pieces (the tablets will not completely dissolve) and drink immediately or within 2 hours. The appearance of the mixture may range from pale yellow to bright yellow. Swallow the tablet dispersion. Do not chew pieces of the tablet. Rinse the container with an additional 120 mL (4 ounces) of water and drink. If the mixture is not consumed immediately, stir the mixture again to ensure that tablets are dispersed.

Table 6-1. Study Treatments

eCRF = electronic case report form; QD = once daily.

^a AMG 510 will be manufactured and packaged by Amgen and distributed using Amgen clinical study drug distribution procedures.

6.1.2 Non-investigational Products

There will be no non-investigational products administered in this study.

6.1.3 Medical Devices

Investigational medical devices will not be used in this study.

Other non-investigational medical devices may be used in the conduct of this study as part of standard care.

Non-Amgen non-investigational medical devices (eg, syringes, sterile needles), that are commercially available are not usually provided or reimbursed by Amgen (except, for example, if required by local regulation). The investigator will be responsible for obtaining supplies of these devices.

6.1.4 Other Protocol-required Therapies

There are no other protocol-required therapies for this study.

6.1.5 Other Treatment Procedures

Not applicable to the study.

6.1.6 Product Complaints

A product complaint is any written, electronic or oral communication that alleges deficiencies related to the identity, quality, durability, reliability, safety, effectiveness, or performance of a drug(s) or device(s) after it is released for distribution to market or clinic by either (1) Amgen or (2) distributors or partners for whom Amgen manufactures the material. This includes all components distributed with the drug, such as packing drug containers, delivery systems, labeling, and inserts.

This includes any investigational products provisioned and/or repackaged/modified by Amgen. AMG 510 is the investigational product in this study.

Any product complaint(s) associated with an investigational product supplied by Amgen are to be reported according to the instructions provided in the IPIM.

6.1.7 Excluded Treatments, Medical Devices, and/or Procedures During Study Period

The following medications and supplements to be avoided for 14 days prior to enrollment and during the study period unless reviewed and approved by the Principal Investigator and the Amgen Medical Monitor:

- Known strong inducers of CYP3A4 including herbal supplements, such as St. John's wort
- Known CYP3A4 and P-gp-sensitive substrates with a narrow therapeutic window unless approved by Amgen medical monitor
- Proton pump inhibitors (PPI) and H2-receptor antagonists unless approved by Amgen medical monitor

If a subject needs palliative radiotherapy for pain control during the course of the study, all study drugs should be discontinued, and the investigator or designee should notify the sponsor as soon as possible. A subject may be allowed to resume study drug after discussion between the Amgen Medical Monitor and the investigator to determine the appropriateness of treatment resumption.

Subjects must not schedule any major elective surgeries during the treatment period, and for at least 28 days after the last administration of AMG 510. Minor elective surgery may be allowed after discussion with the Amgen Medical Monitor. If a subject undergoes any unexpected surgery during the course of the study, AMG 510 must be discontinued, and the investigator or designee should notify the sponsor as soon as possible. A subject may be allowed to resume AMG 510 only if both the investigator and Amgen Medical Monitor agree to restart study therapy.

Dose Cohort Stopping Rules

The DLRT will recommend stopping or modifying dosing if suspected adverse drug reactions, changes in vital signs, electrocardiogram (ECG), or clinical laboratory results are observed, and these changes pose a significant health risk. The Amgen Medical Monitor may suspend dosing and convene a DLRM at any time based on emerging safety data.

Clinically or medically significant suspected adverse drug reactions, and serious adverse events considered to be related to study procedures will be followed until resolved or considered stable.

The study may be terminated at any point at the discretion of the sponsor.

6.2.2 Dose-limiting Toxicity Definition

A DLT is defined as any adverse event meeting the criteria listed below occurring during the first treatment cycle of AMG 510 (day 1 through day 21) where a relationship to AMG 510 cannot be ruled out.

The grading of adverse events will be based on the guidelines provided in the CTCAE (version 5.0). A DLT is defined as any of the following events during the first treatment cycle and attributable to AMG 510:

- Hematological toxicity
 - febrile neutropenia
 - neutropenic infection

- grade 4 neutropenia
- grade \geq 3 thrombocytopenia for > 7 days
- grade 3 thrombocytopenia with grade \geq 2 bleeding
- grade 4 thrombocytopenia
- grade 4 anemia
- Non-hematological toxicity
 - grade \geq 4 vomiting or diarrhea
 - grade 3 diarrhea or grade 3 vomiting lasting more than 3 days despite optimal medical support
 - grade \geq 3 nausea for 3 days or more despite optimal medical support
 - any other grade \geq 3 adverse event

Dose-limiting toxicity-evaluable is defined as completion of 80% of AMG 510 doses within the first treatment cycle (ie, 21 days). A subject who experiences a DLT within the first cycle is DLT-evaluable regardless of number of doses taken. If a subject is withdrawn from the study for any reason other than a DLT prior to completion of the 21-day safety observation period, a replacement subject (if applicable) will be assigned the same dose as the replaced subject.

6.2.3 Dosage Adjustments, Delays, Rules for Withholding or Restarting, Permanent Discontinuation

6.2.3.1 Amgen Investigational Product: AMG 510

Subjects experiencing any treatment-related toxicity meeting the DLT definition will not receive additional AMG 510 treatment and will be followed until resolution of the event or toxicity. Subjects will be withdrawn from AMG 510 treatment and will be treated as deemed appropriate by the investigator or treating physician. In subjects who received the 960 mg dose level with a favorable response to treatment, an option to continue at the same dose level or the lower dose of 480 mg according to the dose modification guidelines in Table 6-2 can be considered.

The reason for dose modification of AMG 510 is to be recorded on each subject's eCRF. Dose reduction levels of AMG 510 for toxicity management of individual subjects are provided in Table 6-2. Up to 2 dose reductions are allowed. Dose reductions below 240 mg are not allowed.

AMG 510 Doses (mg QD)				
Starting Dose	Dose -2			
960	480	240		

Tuble 0-2. Doge Decrements for Amo 010	Table 6-2.	Dose	Decrements	for	AMG	510
--	------------	------	-------------------	-----	-----	-----

QD = once daily

AMG 510 will be discontinued, or dosage reduced in the event of toxicity that, in the opinion of the investigator, warrants the discontinuation, or dose reduction as indicated in Table 6-3. Subjects who experience an adverse event requiring dose reductions below 240 mg should be permanently discontinued from AMG 510 treatment.

If day 1 of a cycle is delayed, day 1 of subsequent cycles should be adjusted accordingly to maintain the 21-day cycle duration. However, if a within-cycle dose is held the missed dose will not be made up and day 1 of subsequent cycles should not be adjusted.

	Recommended Action		
Toxicity	Hold Until:	Restart Dose:	
Grade ≥ 3 nausea, vomiting, or diarrhea lasting longer than 3 days despite optimal medical support	Recovery to grade 1 or less or to baseline grade	Resume dosing at 1 dose lower ^a	
Suspected interstitial lung disease (ILD)/pneumonitis	ILD/pneumonitis confirmed or excluded	 If confirmed, permanently discontinue AMG 510 If excluded, restart at same dose if no other AMG 510 dose modification guidelines are applicable 	
Any other drug-related toxicity \geq grade 3^{b}	Recovery to grade 1 or less or to baseline grade	Resume dosing at 1 dose lower ^a	

 Table 6-3. AMG 510 Dose Modification Guidelines for Hematologic and Non-hematologic Toxicities

^a Subjects may be resumed at a dose lower than the recommended restarting dose after discussion with the medical monitor.

^b For suspected hepatotoxicity, refer to Section 6.2.4 and Section 11.7.

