6.2.4 Hepatotoxicity Stopping and Rechallenge Rules

Refer to Section 11.7 for details regarding drug-induced liver injury guidelines, as specified in the *Guidance for Industry Drug-Induced Liver Injury: Premarketing Clinical Evaluation, July* 2009.

Guidelines for management and monitoring of subjects with increased AST, ALT, or alkaline phosphatase are outlined in Table 6-4.

	Table 6-4. AMG 5	10 Hepatotoxicity Gui	delines		
 If the conditions for permanent discontinuation are met (below): Subject to be permanently discontinued AST or ALT > 3 x ULN and INR > 1.5 x ULN (for subjects not on anticoagulation therapy) in the presence of no important alternative causes for elevated AST/ALT values OR					
CTCAE Grade	AMG 510 Action	Medical Management	Monitoring and Follow-up		
Grade 2 AST or ALT and ALP ≤ 8 x ULN with no clinical symptoms consistent with hepatitis (right upper quadrant pain/tenderness, fever, nausea, vomiting, and jaundice)	Continue	Consider steroids ^b	Closely monitor liver function tests		
	First Occurrence		Closely monitor liver function tests		
Grade 2 AST or ALT	Withhold	Initiate steroids ^b	 Await resolution to baseline or grade 1 and resolution or improvement of hepatitis symptoms Restart at 1 dose level reduction^{c, e} 		
with symptoms Or	Second Occurrence		Closely monitor liver function tests		
Grade 3 or 4 AST or ALT Or	Withhold	Initiate steroids ^b	 Await resolution to baseline or grade 1 and resolution or improvement of hepatitis symptoms Resume at an additional 1 dose level reduction only with MEDICAL MONITOR approval^{c, e} 		
8x ULN ALP ^d	Third Occurrence				
	Permanently		NOT APPLICABLE		

Table 6-4. AMG 510 Hepatotoxicity Guidelines

ALP = alkaline phosphatase; ALT = alanine aminotransferase; AST = aspartate aminotransferase; CTCAE = Common Terminology Criteria for Adverse Events; INR = international normalized ratio; LFT = liver function test; TBL = total bilirubin; ULN = upper limit of normal

^a If increase in AST/ALT is likely related to alternative agent, discontinue causative agent and await resolution to baseline or grade 1 prior to resuming AMG 510.

^b For example: prednisone 1.0 to 2.0 mg/kg/day, dexamethasone equivalent, or methylprednisolone equivalent, followed by a taper. The taper may occur after restarting AMG 510.

^c Close monitoring at restart (eg, daily LFTs x 2, then weekly x 4). AMG 510 dose may be increased after discussion with medical monitor.

discontinue AMG 510

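### After a dose-limiting toxicity, Protocol Section 6.2.3.1 withdraws the subject from AMG 510, but Tables 6-3 and 6-4 say hold and then resume for overlapping events

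*Protocol*

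**What the plan says.** Section 6.2.2 of the protocol defines a DLT as a listed event in cycle 1, day 1 to day 21, for which a relationship to AMG 510 cannot be excluded. Section 6.2.3.1 then says "Subjects experiencing any treatment-related toxicity meeting the DLT definition will not receive additional AMG 510 treatment" and that such subjects are withdrawn from AMG 510. The same paragraph adds: "In subjects who received the 960 mg dose level with a favorable response to treatment, an option to continue at the same dose level", or at 480 mg, can be considered.

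Later in the same subsection, discontinuation or reduction is tied to toxicity that, "in the opinion of the investigator, warrants the discontinuation, or dose reduction as indicated in Table 6-3". Table 6-3 is titled "Dose Modification Guidelines for Hematologic and Non-hematologic Toxicities". Two of its rows say to hold until recovery to grade 1 or baseline and then "Resume dosing at 1 dose lower":

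- grade 3 or higher "nausea, vomiting, or diarrhea lasting longer than 3 days despite optimal medical support";
- "Any other drug-related toxicity" of grade 3 or higher.

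A footnote sends suspected hepatotoxicity to Sections 6.2.4 and 11.7. In Section 6.2.4, Table 6-4 says to withhold at a first occurrence of "Grade 3 or 4 AST or ALT" and, after resolution, to restart one dose level down. Section 11.7 requires the subject, the investigator and the sponsor all to agree to a hepatic rechallenge. It forbids rechallenge only when the Table 11-2 permanent-discontinuation criteria are met, and it does not mention DLTs.

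**The concern.** An investigator whose subject has, say, a drug-related grade 3 non-hematological event on day 10 finds two instructions. One withdraws the subject; the other holds dosing and then resumes it. The choice decides whether the subject is re-exposed to study drug after a dose-limiting toxicity, in a trial whose primary objectives include safety and tolerability.

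It also affects planned outputs. The same event would be reported under adverse events leading to withdrawal of investigational product (Protocol Section 9.4.2.3.2, SAP Section 9.6.2) or under dose modifications with reasons (SAP Section 9.6.7), depending on the passage the site followed. Follow-up would differ as well. The safety follow-up visit is the subject's end of study visit (Protocol Section 8.1.4), and treatment-emergent events are counted up to end of study (SAP Section 5).

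**Working it through.** **1. Do the triggers overlap?** For events on days 1 to 21 attributed to AMG 510:

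| Event | DLT under Section 6.2.2? | Section 6.2.3.1 | Table 6-3 or 6-4 |
|---|---|---|---|
| Grade 3 vomiting or diarrhea, over 3 days despite support (grade 4 at any duration) | Yes | Withdraw | Over 3 days: hold, resume lower |
| Grade 3 or higher nausea, over 3 days despite support | Yes (criterion is 3 days or more) | Withdraw | Hold, resume lower |
| Other non-hematological event, grade 3 or higher | Yes (catch-all) | Withdraw | Hold, resume lower |
| First grade 3 or 4 AST or ALT recorded as an adverse event | Yes (catch-all) | Withdraw | Withhold, restart one level down |
| Grade 4 neutropenia | Yes | Withdraw | Hold, resume lower |
| Grade 3 anemia | No | Not triggered | Hold, resume lower |
| Confirmed ILD/pneumonitis, or permanent-discontinuation criteria met | Not needed | – | Discontinue; no conflict |

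Liver values are within scope because Section 8.2.5 counts a laboratory change that requires treatment or an adjustment of therapy as an adverse event. Neither table excludes cycle 1 or DLTs.

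**2. Does the 960 mg option reconcile the texts?** No.

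- It depends on a favorable response; the tables depend on recovery from the toxicity.
- It allows the same dose level; Table 6-3 says one dose lower.
- It is limited to subjects who received 960 mg; the rows of Tables 6-3 and 6-4 carry no such limit.
- Favorable response is undefined. Section 8.2.2 schedules the first post-baseline scan at 6 ± 1 weeks, so not before week 5, whereas the DLT window closes at week 3. Unless a scan is done early at the physician's discretion, there is no imaging response to rely on when the DLT occurs.

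**3. How often could it arise?** The only related figure is in Section 9.2: 47% to 91% chance of at least one DLT among 6 evaluable subjects at true rates of 10% to 33%. It reproduces:

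- 1 − (1 − 0.10)^6 = 0.469
- 1 − (1 − 0.33)^6 = 0.910

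That is the chance of any DLT, hence an upper bound here. Let p be the true DLT rate and s the share of DLTs that fall in a hold-then-resume row. The documents do not give s, so 0.25 to 1 is assumed.

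P(at least 1 of 6 meets the conflict) = 1 − (1 − s·p)^6

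| p | s = 0.25 | s = 0.50 | s = 0.75 | s = 1 |
|---|---|---|---|---|
| 0.10 | 0.141 | 0.265 | 0.374 | 0.469 |
| 0.33 | 0.404 | 0.661 | 0.818 | 0.910 |

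Section 4.3 reports no DLTs at the exposures studied in the global trial, so lower rates were also tried, as an assumption:

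| p | s = 0.25 | s = 1 |
|---|---|---|
| 0.01 | 0.015 | 0.059 |
| 0.05 | 0.073 | 0.265 |

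One affected subject is 1/6 = 17% of a group of 6, or 1/12 = 8% of a group of 12.

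**4. Follow-up.** If the last dose is by day 21, the safety follow-up visit falls at the latest on day 21 + 30 + 7 = 58. Section 4.4.2 estimates 6 to 12 months of treatment for subjects who continue.

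**5. Is the DLT decision affected?** No. Under Section 6.2.2 a subject with a DLT is evaluable however many doses were taken, so the count and the six-subject review are the same whichever passage is followed.

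**The case against.** The strongest reply is that the texts can be read together. The withdrawal sentence is mandatory and specific to DLTs, while the tables are titled guidelines and the Table 6-3 columns give recommended actions. On that reading the sentence governs cycle 1 DLTs and the tables govern everything else. This is reasonable, but no passage says it, and Section 6.2.3.1 itself leaves discontinuation or reduction per Table 6-3 to the investigator's opinion.

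Several narrower points stand in part:

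- **Hepatic events.** The unanimity rule in Section 11.7 means a site cannot re-dose after hepatotoxicity on its own reading. It does not tell the site or the sponsor which text applies to a hepatic DLT.
- **Dose ladder.** Tables 6-3 and 6-4 refer to dose steps, and the only starting dose legible in Table 6-2 is 960 mg. That narrows the contrast with the 960 mg option on starting dose, but not the contrast on its condition or on the same-dose allowance.
- **Edges of the overlap.** Grade 3 vomiting or diarrhea of 3 days or less is not a DLT by duration, yet might be placed in the Table 6-3 catch-all row. An event that never recovers leads to no re-dosing under either text. Both points trim the overlap without removing it.
- **Outputs.** The safety tables are descriptive and will record what was done. The derivation is not ambiguous; the treatment decision behind it is.
- **Follow-up.** Section 7.1 asks that subjects who stop treatment stay on study where safe and feasible, Section 6.2.3.1 follows the DLT itself to resolution, and Section 4.4.2 says duration may vary. The day 58 contrast is therefore what the visit schedule implies, not a certainty.
- **Oversight.** Only 2 to 4 sites are planned (Section 4.2.2), and the Medical Monitor may suspend dosing at any time (Section 6.2.1). Divergence is less likely, but neither supplies the missing rule.

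**Conclusion.** The concern holds. For an attributable cycle 1 event that meets the DLT definition and sits in a hold-then-resume row, the protocol gives opposite instructions on re-exposure and no order of precedence, and the 960 mg option rests on a different condition. This bears on subject safety and on how withdrawals and dose modifications are reported. It does not alter the DLT count or the cohort decision, and no hypothesis test depends on it.

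The chance that at least one of the first 6 subjects in a cohort meets the conflict is 14% to 47% at a 10% DLT rate, 40% to 91% at 33%, and 1.5% to 26% at rates of 1% to 5%. These ranges rest on an assumed overlap share of 25% to 100% and, for the last, on assumed DLT rates. They describe meeting an overlapping event, not two sites actually acting differently. The case for correction rests on the contradictory text, not on a particular probability.

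**What to change.** Reconcile Section 6.2.3.1 with Tables 6-3 and 6-4 and Section 11.7 so that a single instruction applies to an event meeting the DLT definition. In particular:

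- state whether Tables 6-3 and 6-4 apply to cycle 1 DLTs;
- define favorable response, including how it is judged inside the DLT window;
- state how the 960 mg option relates to the withdrawal sentence and to the tables.

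Which clinical rule to adopt is the sponsor's decision. The change is to protocol wording only and needs no extra subjects or procedures. It carries the usual amendment steps in Section 11.3: ethics committee submission, approval where required, and re-consent if the consent form changes.

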6.2.4 Hepatotoxicity Stopping and Rechallenge Rules

Refer to Section 11.7 for details regarding drug-induced liver injury guidelines, as specified in the *Guidance for Industry Drug-Induced Liver Injury: Premarketing Clinical Evaluation, July* 2009.

Guidelines for management and monitoring of subjects with increased AST, ALT, or alkaline phosphatase are outlined in Table 6-4.

	Table 6-4. AMG 5	10 Hepatotoxicity Gui	delines		
 If the conditions for permanent discontinuation are met (below): Subject to be permanently discontinued AST or ALT > 3 x ULN and INR > 1.5 x ULN (for subjects not on anticoagulation therapy) in the presence of no important alternative causes for elevated AST/ALT values OR					
CTCAE Grade	AMG 510 Action	Medical Management	Monitoring and Follow-up		
Grade 2 AST or ALT and ALP ≤ 8 x ULN with no clinical symptoms consistent with hepatitis (right upper quadrant pain/tenderness, fever, nausea, vomiting, and jaundice)	Continue	Consider steroids ^b	Closely monitor liver function tests		
	First Occurrence		Closely monitor liver function tests		
Grade 2 AST or ALT	Withhold	Initiate steroids ^b	 Await resolution to baseline or grade 1 and resolution or improvement of hepatitis symptoms Restart at 1 dose level reduction^{c, e} 		
with symptoms Or	Second Occurrence		Closely monitor liver function tests		
Grade 3 or 4 AST or ALT Or	Withhold	Initiate steroids ^b	 Await resolution to baseline or grade 1 and resolution or improvement of hepatitis symptoms Resume at an additional 1 dose level reduction only with MEDICAL MONITOR approval^{c, e} 		
8x ULN ALP ^d	Third Occurrence				
	Permanently		NOT APPLICABLE		

Table 6-4. AMG 510 Hepatotoxicity Guidelines

ALP = alkaline phosphatase; ALT = alanine aminotransferase; AST = aspartate aminotransferase; CTCAE = Common Terminology Criteria for Adverse Events; INR = international normalized ratio; LFT = liver function test; TBL = total bilirubin; ULN = upper limit of normal

^a If increase in AST/ALT is likely related to alternative agent, discontinue causative agent and await resolution to baseline or grade 1 prior to resuming AMG 510.

^b For example: prednisone 1.0 to 2.0 mg/kg/day, dexamethasone equivalent, or methylprednisolone equivalent, followed by a taper. The taper may occur after restarting AMG 510.

^c Close monitoring at restart (eg, daily LFTs x 2, then weekly x 4). AMG 510 dose may be increased after discussion with medical monitor.

discontinue AMG 510

^d There is no limit to the number of AMG 510 re-challenges for isolated alkaline phosphatase elevations that resolve to baseline or grade 1.

^eDose decrements below 240 mg are not allowable.

Page 42 of 109

